6.6.2 Withdrawal from Study

For subjects who withdraw prematurely from the study (eg, due to withdrawal of consent or noncompliance with study procedures), the reason(s) for withdrawal must be recorded on the appropriate page of the electronic case report form (eCRF). If possible, any subject who is

withdrawn from the study will have, at the time of withdrawal, all exit procedures performed (ie, Day 365 safety and efficacy assessments). All clinically significant abnormalities will be followed-up, if possible, until resolved to the satisfaction of the Investigator.

6.6.3 Replacement of Subjects

Subjects will not be replaced after randomization.

6.6.4 Subjects Lost to Follow-up

For subjects who are lost to follow-up (ie, those subjects whose status is unclear because they fail to appear for study visits without stating an intention to withdraw), the Investigator should show "due diligence" by documenting in the source documents steps taken to contact the subject, eg, dates of telephone calls, registered letters, etc.

6.7 Study Suspension or Termination

The Sponsor reserves the right to temporarily suspend or terminate this study at any time. The reasons for temporarily suspending or terminating the study may include but are not limited to the following:

- The incidence or severity of AEs indicates a potential health hazard to subjects.
- Subject enrollment is unsatisfactory.
- Noncompliance that might significantly jeopardize the validity or integrity of the study.
- Sponsor decision to terminate development.

Additional guidance is provided in the Safety and Data Monitoring Committee (SDMC) Charter.

If Sponsor determines that temporary suspension or termination of the study is required, Sponsor will communicate the reasons for taking such action with all participating Investigators (or head of the medical institution, where applicable). When feasible, Sponsor will provide advance notice to all participating Investigators (or head of the medical institution, where applicable) of the impending action.

If the study is suspended or terminated for safety reasons, Sponsor will promptly inform all Investigators, heads of the medical institutions (where applicable), and/or institutions conducting the study. Sponsor or designee will also promptly inform the relevant regulatory authorities of the suspension/termination along with the reasons for such action. Where required by applicable regulations, the Investigator or head of the medical institution must inform the IRB/Independent Ethics Committee (IEC) promptly and provide the reason(s) for the suspension/termination. If the study is suspended for safety reasons and it is deemed appropriate by the Sponsor to resume the study, approval from the relevant regulatory authorities (and IRBs/IECs, when applicable) will be obtained prior to resuming the study.

6.8 End of Study

Once a subject has completed all assessments listed for Visit 15 (Day 365 ± 7 days), the subject will be considered to have completed the study. The study will be completed once the last subject out has completed all Visit 15 or EDV assessments (Day 365 ± 7 days; shown in Table 3).

7 STUDY INTERVENTIONS

7.1 Description of Products

Table 4 provides a description of IP to be used in the study. Details are presented in the following sections.

 Table 4
 Description of Investigational Products

Product	Dose	Frequency	Route	Duration	Manufacturer
VIB4920	1500 mg	Stage I: Q2W x 3 Q4W x 4 Stage II: Q4W x 5	IV	Up to 169 days	MedImmune, LLC
VIB4920 Placebo	0.9% (w/v) saline	Stage I: Q2W x 3 Q4W x 4 Stage II: Q4W x 5	IV	Up to 169 days	Provided by site

IV = intravenous; Q2W = once every 2 weeks; Q4W = once every 4 weeks; w/v = weight/volume.

7.1.1 VIB4920

7.1.1.1 Formulation, Storage, Preparation, and Handling

VIB4920 is formulated at 100 mg/mL VIB4920 in mM sodium phosphate buffer, mM sucrose, (weight/volume [w/v]) poloxamer 188, pH m. The nominal volume in each vial is 5.0 mL. VIB4920 is a sterile liquid Drug Product (500 mg VIB4920 per vial, nominal) intended for IV infusion following dilution in normal saline.

The IP will be appropriately labeled in accordance with national laws and regulations. VIB4920 is provided with 3 vials per kit.

VIB4920 should not be shaken and requires no special biohazard handling. It must be stored at in refrigerator with adequate temperature monitoring. VIB4920 must not be frozen. It should be stored in the original outer package in a location with limited access.

Each vial selected for dose preparation should be inspected. If there are any defects noted with the VIB4920, the Investigator and site monitor should be notified immediately.

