6.3 Randomization

Prior to randomization, subject eligibility must be confirmed by the MR team (see Section 6.1). Subjects who meet all eligibility criteria, including confirmation of eligibility by the study MR review team, will be randomized. A subject is considered randomized into the study when the Investigator notifies the IXRS that the subject meets eligibility criteria and the IXRS provides the assignment of treatment group and allocates treatment, including IP kit number (Day 1, Baseline [Table 2]). To ensure balanced rates of enrollment for the 2 populations, the Sponsor will implement a procedure where enrollment of subjects in Population #2 at each site is linked to enrollment of Population #1 subjects at the site with a progressively increasing ratio of

Module 5.3.5.1 Clinical Study Protocol VIB4920.P2.S2 - VIB4920 in Subjects with Sjögren's Syndrome Version 3.0 (8Nov2022)

Population #2:Population #1 subjects. At least one subject of the first 2 randomized at each site must be from Population #1.

For details on the MR procedure, see Section 6.1.

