7.1.1.6 VIB4920 Handling and Disposal

The Investigator or designee must return any unused vials of VIB4920 to Sponsor or designee regardless of whether the study was completed or terminated prematurely. At the time of return, the Investigator must verify that unused or partially used study products have been returned and that no study products remain at the site. As an alternative to returning unused study product at the end of the study, the Investigator may destroy unused study medication on site with agreement from Sponsor.

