7.1.2 Placebo

7.1.2.1 Formulation, Storage, Preparation and Handling

Placebo will be 0.9% (w/v) saline provided by the site as 250 mL prefilled IV bags.

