7.2.3 Extent and Maintenance of Blinding

This is a double-blind study in which VIB4920 and the saline placebo are not identical in appearance. For maintaining the blinding of the subjects, Investigator, site staff, Sponsor, Contract Research Organization and staff, a local unblinded pharmacy staff member will be nominated by each site and will have the responsibility of allocating, dispensing and preparing the IP, and covering the IV bags. In addition, a separate unblinded monitor will be used for the oversight of IP management. If treatment allocation for a subject becomes known to the Investigator or other study staff involved in the management of study subjects, the Sponsor must be notified immediately.

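### Vial-defect notices under protocol 7.1.1.1 go to the Investigator, whom 7.2.3 keeps blinded, and could occasionally reveal a subject's treatment

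*Protocol*

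**What the plan says.** Protocol 7.2.3 sets the blinding arrangement. It admits the difficulty: "This is a double-blind study in which VIB4920 and the saline placebo are not identical in appearance". It then sets out who is protected and how: "For maintaining the blinding of the subjects, Investigator, site staff, Sponsor, Contract Research Organization and staff, a local unblinded pharmacy staff member will be nominated". That person allocates and prepares the product and covers the bags, and a separate unblinded monitor oversees product management. If the Investigator learns an allocation, the Sponsor must be told at once.

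Protocol 7.1.1.1 describes VIB4920 as vials supplied three to a kit. On preparation it says "Each vial selected for dose preparation should be inspected", followed directly by "If there are any defects noted with the VIB4920, the Investigator and site monitor should be notified immediately".

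The placebo section, 7.1.2.1, describes no vial: "Placebo will be 0.9% (w/v) saline provided by the site as 250 mL prefilled IV bags".

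Two other places touch the same division of roles:
- Section 6.3 has the Investigator notify the IXRS, after which "the IXRS provides the assignment of treatment group and allocates treatment, including IP kit number". Section 7.2.2 is similar and leaves detail to the IXRS Manual.
- Section 7.1.1.6 lets a designee return unused vials, but at that time "the Investigator must verify that unused or partially used study products have been returned".

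**The concern.** The blind rests on keeping product information with two unblinded roles, because the two products can be told apart by sight. The defect rule sends information that can arise only for VIB4920 to someone outside those roles. If a vial fails inspection while a subject's dose is being made up, and the Investigator is told immediately, the Investigator can infer that the subject's infusion is active.

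The Investigator or another qualified site staff member scores the ESSDAI (protocol 12.2), and protocol 10.5.4 calls it a clinician-reported outcome. Change in ESSDAI at Day 169 is the Population #1 primary endpoint. Knowledge of treatment can influence such a rating, and in Stage I a notice can concern only a subject receiving VIB4920. Because the arms switch at Day 169 (protocol 4.1), knowing one infusion reveals the treatment in both stages.

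**Working it through.** The point is a conflict between rules, so the check is mainly to set them side by side.

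1. **Who may hold product information.** Section 7.2.3 names an unblinded pharmacy staff member and a separate unblinded monitor. The Investigator is listed among those kept blinded.
2. **Who is told of a defect.** Section 7.1.1.1 names the Investigator and the site monitor, with no qualifier. Section 7.1.1.5 does write unblinded when it gives drug accountability to a monitor, so the protocol makes the distinction where it intends it.
3. **What a notice reveals.** The inspection applies to vials already chosen for a dose. VIB4920 is drawn from vials (7.1.1.2); placebo is a prefilled bag (7.1.2.1). A vial defect found at that moment implies active drug for that dose. The text does not require the notice to name a subject, so disclosure depends on whether the recipient can connect it with a dosing visit. An immediate notice on a dosing day makes that possible.
4. **Timing.** Stage I doses fall on Days 1, 15, 29, 57, 85, 113 and 141 (Table 2). All seven precede the Day 169 endpoint visit, so any Stage I notice precedes the primary assessment.
5. **Number of inspections.** Each dose uses 3 vials (7.1.1.2), and Stage I has 7 doses.
   - Population #1: 36 × 7 × 3 = 756 vials.
   - Population #2: 51 × 7 × 3 = 1,071 vials.
   - Together: 1,827 vials.

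   These are opportunities for a notice, not notices. The documents give no defect rate, so no expected number of notices follows.
6. **The plan's own figure.** For Population #1 (36 per arm, difference 3.0, SD 5, two-sided alpha 0.10), the standard error is 5 × √(2/36) = 1.18. The two-sample t-test power is 81.0%, against 80% stated. The minimum detectable difference is 1.96, against 2.0 stated. The figures reproduce, and this point changes neither.
7. **Scale, as illustration only.** Suppose rating bias moved the VIB4920 arm mean by an assumed 0.25, 0.5 or 1.0 ESSDAI points with no true effect. The rejection rate would be 10.7%, 13.0% or 21.7%, against the nominal 10%. A mean shift of 0.25 in 36 subjects needs 36 × 0.25 = 9 points in total, for example 3 subjects each mis-scored by the full design difference of 3.0. The larger shifts need 18 and 36 points, or 6 and 12 such subjects. Isolated notices are unlikely to reach that.

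**The case against.** The strongest reply is that the blind has several layers. Bags are covered, preparation and accountability belong to unblinded staff, and the Sponsor is told if an allocation becomes known. An IP Manual, not available here, may route defect reports correctly. The defect rule also needs two conditions before it discloses anything. This stands as a limit on size. It does not remove the conflict: covering a bag does not redirect a notice, the Sponsor rule acts only after the fact, and the protocol sentence still names the Investigator.

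A reader might infer more than the documents support:

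- **That the IXRS exposes everyone.** Sections 6.3 and 7.2.2 do not say who receives the output, and 7.2.3 gives allocation to the unblinded pharmacist. Section 7.2.1 uses IP for either product, so kit numbers cannot be taken as confined to VIB4920. This is unclear wording, not a shown leak.
- **That verifying vial return unblinds subjects.** Section 7.1.1.6 concerns site stock and names no subject.
- **That the delay notice in 7.2.1 has the same fault.** It applies to both products and by itself discloses nothing.
- **That ESSPRI is biased directly.** The notice goes to the Investigator. Subjects complete ESSPRI themselves, electronically and before other procedures (6.4.1), so any effect is indirect.
- **That following the rule creates a major deviation under SAP 3.2.** That item covers a blind broken by the site investigator. Receiving a pharmacy notice is not plainly that.

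**Conclusion.** The contradiction between 7.1.1.1 and 7.2.3 is real. Following the defect rule as written could unblind individual subjects to the Investigator. The direct risk is to the clinician-rated ESSDAI in Population #1.

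It would be too strong to say that following the handling rules unblinds subjects in general. Disclosure requires a defective vial and a notice traceable to a dosing visit. It also rests on placebo having no vial, which is what the protocol describes.

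The effect cannot be sized from the documents and is likely small. Sample size, alpha and the analysis model are unaffected.

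**What to change.** In 7.1.1.1, send defect notices to the unblinded pharmacist and the unblinded monitor in place of the Investigator and site monitor.

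As secondary alignment with 7.2.3:
- In 6.3 and 7.2.2, state that the IXRS treatment-group and kit output goes only to unblinded staff.
- In 7.1.1.6, let the unblinded pharmacist verify vial return while the study is blinded.

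Section 7.2.1 needs no change on this account. The cost is wording in four protocol sections and a check that the IXRS access settings and the IP Manual agree. Both roles already exist under 7.2.3, so no staff are added.

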7.1.1.2 Dose Preparation

VIB4920 is supplied as a sterile liquid in a 6R glass vial at a nominal fill volume of 5.0 mL, stoppered with 20 mm Teflon-coated elastomeric stopper, and sealed with flip-off cap overseal.

No incompatibilities between VIB4920 and the components recommended for IV infusion (ie, polyolefin IV bags for IV infusion, non-diethylhexyl phthalate infusion lines, and syringes used for dose preparation) have been observed.

VIB4920 does not contain preservatives and any unused portions must be discarded. Preparation of IP and IV bags is to be performed aseptically.

Prepared VIB4920 IV Bags may be stored refrigerated at 2-8°C for up to 24 hours and/or at room temperature for up to 4 hours. The total allowable in-use storage time from the time of the first vial puncture of VIB4920 to IV bag administration is 24 hours.

DO NOT FREEZE. If storage time exceeds these limits, a new dose must be prepared from new vials.

Three vials, one 250 mL IV bag containing 0.9% (w/v) saline (weight/volume [w/v]), and one IV infusion pump is required for administration of each 1500 mg dose of VIB4920.

The dose preparation steps are as follows:

- For each 1500 mg IV dose, 15.0 mL of 0.9% (w/v) saline should be removed from a prefilled 250 mL IV bag.
- 15.0 mL of VIB4920 will be obtained from three (3) 500 mg vials by withdrawing 5.0 mL from each vial. Use a new needle for each withdrawal.
- IP should be added to the saline bag.
- Gently mix the contents of the IV bag. The saline bag should then be inspected to ensure the solution is clear.
- Prepared bags will be covered to protect blinding.

During preparation of the IP for infusion, the capacity of the tubing should be calculated in order to adjust the volume of IP solution needed to prime the IV tubing. This step is also necessary because the same volume of saline will be needed to flush the IV tubing at the completion of the infusion in order to deliver the complete volume of IP solution. Because the IV tubing contains IP solution, the saline flush must be infused using the same infusion rate as that used for the IP solution in the infusion bag.

For example, if the IV tubing capacity is 15 mL, the IV tubing should be primed with 15 mL of IP solution from the infusion bag before initiating the infusion. Once the infusion bag is empty, the IV tubing should be flushed with at least 15 mL of 0.9% (w/v) saline via the infusion pump at the same rate as dosing. The start time of the infusion will be the time when infusion of the IP solution from the infusion bag (with IV tubing primed with IP solution) is started. The stop time of the infusion will be the time when the IV tubing has been flushed with a volume of 0.9% (w/v) normal saline equivalent to IV tubing capacity (eg, 15 mL for the example above) to administer the residual IP solution.

7.1.1.3 Dosing and Administration

Both Populations #1 and #2 will receive the following treatment regimen:

- Treatment group 1 will receive 1500 mg VIB4920 as an IV infusion, Q2W x 3, then Q4W for 4 additional doses (Stage I). Starting on Day 169 subjects will receive placebo Q4W for 5 doses (Stage II).
- Treatment group 2 will receive placebo as an IV infusion Q2W x3, then Q4W for 4 additional doses (Stage I). Starting on Day 169 subjects will receive VIB4910 1500 mg Q4W for 5 doses (Stage II).

An experienced and qualified staff member will place the IV access.

IP will be infused using an IV infusion pump. During Stage I each subject must receive the entire volume of IP solution in the IV bag over at least 90 minutes (approximately 2.8 mL/min). IP must be infused through a low-protein binding 0.2- or 0.22-line filter. Vital signs will be obtained prior to the start of each IP infusion. For Stage II, infusions can be administered over at least 60 minutes (approximately 4.2 mL/min).

A physician must be present at the site or immediately available to respond to emergencies during administration of IP. Fully functional resuscitation facilities should be available.

Further information on IP preparation and administration is provided in the IP Manual.

7.1.1.4 Peri- and Post-Administration Observations

On the first 2 dosing days of both Stage I (Day 1 and Day 15) and Stage II (Day 169 and Day 197) vital signs will be measured within 30 minutes prior to the start of infusion, every 30 minutes (\pm 5 minutes) during the infusion, at the end of the infusion (\pm 5 minutes), then at 1 hour and 2 hours after the end of infusion (\pm 10 minutes). On subsequent dosing days, vital signs will be measured within 30 minutes prior to the start of infusion, every 30 minutes (\pm 5 minutes), at the end of the infusion (\pm 5 minutes) and 30 minutes after the end of the infusion (\pm 5 minutes). At the end of these observation periods, subjects can be discharged if they are stable.

7.1.1.5 Investigational Product Accountability

The study IXRS system will be used by clinical sites to acknowledge receipt of study drug. Damaged shipments will be replaced. Study site staff will maintain a record of the IP received, dispensed, administered, and destroyed. All records will be maintained with controlled access. An unblinded study monitor will perform drug accountability and compliance monitoring during the study. The Investigator will administer the study product only to subjects included in this study and according to the procedures established in this clinical study protocol. Each administration of study product will be documented and transferred to the eCRF.

7.1.1.6 VIB4920 Handling and Disposal

The Investigator or designee must return any unused vials of VIB4920 to Sponsor or designee regardless of whether the study was completed or terminated prematurely. At the time of return, the Investigator must verify that unused or partially used study products have been returned and that no study products remain at the site. As an alternative to returning unused study product at the end of the study, the Investigator may destroy unused study medication on site with agreement from Sponsor.

7.1.2 Placebo

7.1.2.1 Formulation, Storage, Preparation and Handling

Placebo will be 0.9% (w/v) saline provided by the site as 250 mL prefilled IV bags.

7.1.2.2 Dosing and Administration

For each dose of placebo, one 250 mL IV bag containing 0.9% (w/v) saline (weight/volume [w/v]) and one IV infusion pump is required for administration.

7.2 Treatment Assignment and Bias Minimization

7.2.1 Treatment Allocation

Subjects will be randomized in a 1:1 ratio to receive either VIB4920 or placebo.

IP (VIB4920 or placebo) must be administered the same day the IP is assigned. If there is a delay in the administration of IP such that it will not be administered within the specified timeframe, the study monitor must be notified immediately.

7.2.2 Randomization Strategy and Procedure

An IXRS will be used for randomization to a treatment group and assignment of IP kit numbers. A subject is considered randomized into the study when the Investigator notifies the IXRS that the subject meets eligibility criteria and the IXRS provides the assignment of treatment group.

Additional details will be provided in the IXRS Manual.

7.2.3 Extent and Maintenance of Blinding

This is a double-blind study in which VIB4920 and the saline placebo are not identical in appearance. For maintaining the blinding of the subjects, Investigator, site staff, Sponsor, Contract Research Organization and staff, a local unblinded pharmacy staff member will be nominated by each site and will have the responsibility of allocating, dispensing and preparing the IP, and covering the IV bags. In addition, a separate unblinded monitor will be used for the oversight of IP management. If treatment allocation for a subject becomes known to the Investigator or other study staff involved in the management of study subjects, the Sponsor must be notified immediately.

7.2.4 Unblinding Procedures

7.2.4.1 Unblinding in the Event of a Medical Emergency

In the event of a medical emergency, the Investigator may unblind an individual subject's IP allocation. Instructions for unblinding an individual subject's IP allocation are contained in the IXRS manual. In general, unblinding should only occur if management of the medical emergency would be different based on the subject having received IP. In the majority of cases, the management of a medical emergency would be the same whether or not IP was received by the subject. If this was the case, the IP allocation should not be unblinded.

7.2.4.2 Unblinding for Interim Analysis and Primary Analysis

An interim analysis will be conducted for each population after all subjects have completed the Day 85 visit for that population, and the primary analysis will be conducted for each population after all subjects have completed the Day 169 visit for that population (see Section 10.6). To ensure the blinding of each subject's treatment assignment throughout the study, both the interim

analysis and the primary analysis will be performed by a limited number of Sponsor personnel who are not involved in the conduct of the study. Study site personnel, subjects, and Sponsor personnel directly associated with the conduct of the study will remain blinded to the treatment assignment for individual subjects until the completion of the study. Any communications of unblinded results will be documented in an unblinding memo. Population-based treatment group level results may be released after completion of primary analysis.

